10.3 Analysis Population

The following analysis populations will be used:

- Full Analysis Set (FAS) is defined as all subjects who have received at least one dose of study medication.

CONFIDENTIAL

STUDY DRUG: NIVOLUMAB

SARAH CANNON DEVELOPMENT INNOVATIONS STUDY NUMBER:

FINAL PROTOCOL DATE: 07 FEB 2020

BMT 24

VERSION 7

- Efficacy-Evaluable Population (EFF) is defined as all subjects receiving at least two cycles of study medication.
- Safety Population (SAF) is defined as all patients who have received at least one dose of study treatment. This population will be used for the safety analysis.

10.4 Data Analysis

Descriptive statistics, including mean, median, standard deviations and ranges for all continuous measures will be tabulated and reported. Percentages and frequencies for all categorical measures will also be presented. Time-to-events endpoints will be reported using Kaplan-Meier estimates, with 95% a CI for median time to event.

10.4.1 Demographics and Baseline Characteristics

Demographic and baseline disease characteristics will be summarized. Data to be tabulated will include demographic features such as age, sex and race, as well as disease-specific characteristics.

The number and percentages of patients screened, randomized, treated, completed the treatment/study and withdrawn from treatment/study for any reasons will be presented.

10.4.2 Efficacy Analysis

The primary efficacy analysis will be performed using the FAS. Sensitivity analyses will be performed using the Efficacy-Evaluable Population (EFF).

- Progression-Free Survival (PFS), defined as the time from the first day of study drug administration (Day 1) to disease progression as defined by the Recommendations for Initial Evaluation, Staging, and Response Assessment of Hodgkin and Non-Hodgkin Lymphoma: The Lugano Classification (Cheson et al. 2014, see Appendix F), or death on study. Patients who are alive and free from disease progression will be censored at the date of last tumor assessment.

For PFS Kaplan-Meier curves will be generated and the median time to event and the associated 95% CI be provided. Kaplan-Meier estimates will also be produced for the following specified time points: 12 months and 24 months. The hazard ratio and the 95% CI for these endpoints between the two treatment groups will be calculated.

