Section 5.0 Study Design Five of the forty patients to be enrolled on the study will be enrolled to a control group.

Section 5.4.2 Immune Recovery versus Control Group Section added to detail study schedule for control patients.

CONFIDENTIAL

STUDY DRUG: NIVOLUMAB

SARAH CANNON DEVELOPMENT INNOVATIONS STUDY NUMBER:

FINAL PROTOCOL DATE: 07 FEB 2020

VERSION 7

BMT 24

BMT 24 PROTOCOL SYNOPSIS

Title of Study:	A Phase II Single Arm Study of Nivolumab as Maintenance Therapy after Autologous Stem Cell Transplantation in Patients with Hodgkin Lymphoma at Risk of Relapse or Progression	
Sarah Cannon Development Innovations Study Number:	BMT 24	
Sponsor:	Sarah Cannon Development Innovations, LLC – Nashville, TN	
Study Duration:	The total duration of the study is planned to be 4 years (2 years enrollment and 2 years maximum follow-up).	Phase of Study: II
Study Centers:	This study will be conducted at 6 study sites.	
Number of Patients:	Up to 40 patients are planned to be enrolled in this study: 35 will receive study treatment and 5 patients will receive standard-of-care procedures and treatment both pre- and post-transplant.	
Objectives:	
Primary Objective The primary objective of this study is to:
 
 • Evaluate safety and tolerability of nivolumab as maintenance early after autologous stem cell transplant (ASCT) in patients with Hodgkin Lymphoma (HL) 
Secondary Objectives The secondary objective of this study is to:
 
 • Evaluate PFS at 12 months post-transplant when nivolumab is administered as maintenance in patients with HL after ASCT 
Exploratory Objectives The exploratory objectives of this study are to:
 
 • Correlate efficacy of nivolumab when given as maintenance after ASCT with programmed cell death protein-1 (PD-1) expression and other immune effector and regulatory cells • Correlate positron emission tomography (PET)- computed tomography (CT) negativity with PFS 	
Study Design:	This is a Phase II single-arm open-label study of nivolumab as maintenance therapy after ASCT in patients with HL at risk of relapse or progression.	

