2.2 Secondary Objectives

The secondary objective of this study is to:

- Evaluate PFS at 12 months post-transplant when nivolumab is administered as maintenance therapy in patients with HL after ASCT

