7. STUDY ASSESSMENTS AND EVALUATIONS

7.1 Overview

All patients should visit the study center on the days specified within this protocol. The complete Schedule of Assessments for this study is shown in Appendix E. The baseline physical examination, medical history, ECOG PS, complete blood count (CBC) with differential and platelets, comprehensive metabolic profile (CMP), and prothrombin time (PT)/partial thromboplastin time (PTT)/International Normalized Ratio (INR) should be done ≤ 7 days prior to initiation of treatment. A pregnancy test must be performed within 72 hours of Cycle 1 Day 1. PET-CT scans should be performed ≤ 6 weeks prior to initiation of treatment. ECG and research samples should be performed ≤ 28 days prior to initiation of study treatment.

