7.5 Response Assessment

Patients should have PET-CT scans done per institution standard of care. PET-CT scans are required 1-3 months post-ASCT prior to initiation of therapy, 6 months post-ASCT, and 1 year post-ASCT. If there is prior evidence of bone marrow involvement, patients should also have bone marrow biopsy performed if in CR at these staging visits to document response.

Patients discontinuing therapy early receiving >6 cycles with measurable disease at baseline are recommended to have an EOT PET-CT. Patients ending treatment early need to have a PET-CT at 1 year post-ASCT unless patient progresses or starts a new therapy.

CONFIDENTIAL

STUDY DRUG: NIVOLUMAB

SARAH CANNON DEVELOPMENT INNOVATIONS STUDY NUMBER:

FINAL PROTOCOL DATE: 07 FEB 2020

BMT 24

VERSION 7

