9. RESPONSE EVALUATIONS AND MEASUREMENTS

Lymphoma progression will be assessed using the Recommendations for Initial Evaluation, Staging, and Response Assessment of Hodgkin and Non-Hodgkin Lymphoma: The Lugano Classification (Cheson et al. 2014, see Appendix F). Progression will be assessed 6 months post-ASCT and 1 year post-ASCT.

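### The objective measures PFS from transplant but the analysis measures it from first dose, so no required scan reaches the 12-month estimate on the analysis clock

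*Combined protocol and SAP*

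**What the plan says.** Section 2.2 sets the only secondary objective: "Evaluate PFS at 12 months post-transplant when nivolumab is administered as maintenance therapy in patients with HL after ASCT". The synopsis says the same. Section 10.4.2 starts the clock elsewhere: PFS is "defined as the time from the first day of study drug administration (Day 1) to disease progression", or death. It adds that "Kaplan-Meier estimates will also be produced for the following specified time points: 12 months and 24 months", and that "Patients who are alive and free from disease progression will be censored at the date of last tumor assessment".

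Section 5 places the first dose 45-180 days after transplant; the synopsis adds ±10 days. Tumor assessments follow the transplant clock. Section 7.5 states that "PET-CT scans are required 1-3 months post-ASCT prior to initiation of therapy, 6 months post-ASCT, and 1 year post-ASCT", with other scans left to institutional standard of care. Section 9 agrees: "Progression will be assessed 6 months post-ASCT and 1 year post-ASCT". In Appendix E the Follow-Up column has no PET-CT. Section 7.6 continues follow-up for up to 2 years after the last dose, and lets a phone call for survival and new lymphoma treatment suffice after the 1-year assessment. Section 10.5.1 triggers the final analysis on the 12-month post-transplant assessment.

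Section 10.2 tests 12-month PFS of 50% against 70% without naming an origin. It uses a two-sided one-sample log-rank test, 36 evaluable subjects, exponential PFS, 18 months of enrollment and 12 months of further follow-up. It states an event probability of 0.4579, 16 events and 80.3% power. The synopsis plans 2 years of enrollment and 35 treated patients.

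**The concern.** The objective, the required scans and the final-analysis trigger all run from transplant; the PFS definition alone runs from first dose. The two origins differ by 1.5 to 5.9 months per patient. Followed as written, section 10.4.2 does not estimate the quantity in section 2.2. Event-free patients with only the required scans are all censored before month 12 on the analysis clock.

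Safety is the primary objective, but PFS is the only efficacy endpoint and carries the plan's only hypothesis and sample size. A reported 12-month PFS could mean either quantity, and it would be judged against a 50% null that is tied to neither.

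**Working it through.** **1. The plan's own figures.** Exponential hazards per month: null ln 2/12 = 0.05776; alternative −ln(0.7)/12 = 0.02972 = h; ratio 0.5146. With uniform accrual over 18 months and 12 months of further follow-up, the event probability is 1 − (e^(−12h) − e^(−30h))/(18h) = 0.4579, as stated. Times 36 this is 16.5 events (stated as 16).

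Power by the asymptotic one-sample log-rank formula is Φ[(√n(v1 − v0) − 1.96√v1)/σ]. Here v0 = 0.4579, v1 = 0.4579/0.5146 = 0.8898 and σ ≈ 0.87. This gives Φ[(2.59 − 1.85)/0.87] = 80.3%, as stated. These figures give every patient 12 to 30 months of progression follow-up.

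**2. Where the last required scan falls** (365 days, 30.4375 days per month):

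| First dose | 1-year scan, months after Day 1 |
|---|---|
| Day 45 | (365 − 45)/30.4375 = 10.5 |
| Day 180 | (365 − 180)/30.4375 = 6.1 |
| Day 35 (synopsis window) | 10.8 |
| Day 190 (synopsis window) | 5.7 |

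Section 7.1 adds that "PET-CT scans should be performed ≤ 6 weeks prior to initiation of treatment". If a single pre-treatment scan must also fall 1-3 months post-transplant, first dose comes by about Day 91 + 42 = 133. The last required scan is then (365 − 133)/30.4375 = 7.6 to 10.5 months after Day 1. Every value is below 12.

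Conversely, month 12 after Day 1 is 12 + 45/30.4375 = 13.5 to 12 + 180/30.4375 = 17.9 months post-transplant. Month 24 is 25.5 to 29.9.

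**3. Effect of the clock on the 12-month value.** Assume exponential PFS, patients progression-free at Day 1 and start days uniform over Day 45-180. The time from first dose to 1 year post-transplant is then uniform on 6.08 to 10.51 months. The mean progression-free probability at 1 year post-transplant is (e^(−6.08h) − e^(−10.51h))/(4.435h):

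| Hazard | 12 months after Day 1 | 12 months post-transplant |
|---|---|---|
| Null | 50% | 62.1% |
| Alternative | 70% | 78.2% |

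With starts ending at Day 133 the last column is 59.3% and 76.4%.

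**4. Power by length of progression ascertainment.** Same assumptions, no dropout, n = 35-36, two-sided 0.05. The statistic is (O − E)/√E with null events counted from first dose, and power is by simulation (60,000 trials). Events to the 1-year scan are n × (1 − 0.782).

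| Progression ascertained until | Events | Power |
|---|---|---|
| Each patient's 1-year post-transplant scan | 7.6-7.8 | 47-48% |
| Same, starts end by Day 133 | 8.3-8.5 | 51-52% |
| 12 months after Day 1 | 10.5-10.8 | 63-64% |
| Last patient's 1-year scan, 18-month accrual (10.2) | 14.0-14.4 | 76-77% |
| Last patient's 1-year scan, 24-month accrual (synopsis) | 15.5-15.9 | 80-81% |
| 12-30 months, as 10.2 assumes | 16.0-16.5 | 81-83% |

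Only the first two rows rest on required scans alone.

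**The case against.** **This is one defect, not two.** If PFS is timed from transplant, the 1-year scan lands on the 12-month landmark. That stands. The shortfall at 12 months follows from the origin conflict and is not a separate fault in the scan schedule. Only the 24-month estimate lacks a required scan on either clock.

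**Other scans may exist.** A reader might infer that there will be no tumor data at 12 months after Day 1. The documents do not support that. Section 7.5 expects standard-of-care scans, section 10.4.2 censors at the last assessment whether or not it was required, and the phone call in section 7.6 is optional. Later ascertainment is unspecified, not absent. It could differ by site, and the plan cannot count on it.

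**Power need not fall.** A reader might infer that the true power is well below 80.3%. That holds under some readings only. With the synopsis's 2-year enrollment and ascertainment to the last patient's 1-year scan, power is 80-81%. The 47-48% needs no progression to be captured after each patient's own 1-year scan and starts spread to Day 180. If starts cluster at Day 45-90 (an assumption), the same cut gives 54-56%.

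**Timing from transplant has its own problem.** Patients must reach first dose to be counted, so earlier time carries no observable event. In addition, no eligibility criterion in sections 3.1-3.2 requires freedom from progression between transplant and first dose. Both need a rule.

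**Conclusion.** The point holds and should be fixed. The conflict of origins and the 6.1-10.5 months (5.7-10.8 with the synopsis window) are read directly from the text and need no model. No required scan supports the 12-month estimate on the analysis clock, and none supports the 24-month estimate on either clock.

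The clock moves the 12-month value by about 12 points under the null and 8 under the alternative, against a design difference of 20. This rests on exponential PFS, uniform starts over Day 45-180 and patients progression-free at Day 1.

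The stated power reproduces, but it depends on progression follow-up that the required scans alone do not deliver. Across the readings above it runs from 47% to 81%, and the plan does not say which applies. Because safety is primary, this does not threaten the main objective.

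**What to change.** - Use one time origin in sections 2.2, 10.2 and 10.4.2, and state the origin of the 50% null.
- To keep the stated objective, time PFS from transplant. In the one-sample log-rank test, let each patient enter the risk set at first dose and count expected null events only from then. State how a progression between transplant and first dose is handled in the analysis.
- Report the share of treated patients progression-free at the 1-year post-transplant scan with its confidence interval, and count progressions found at that scan. At n = 35 the half-width is about 1.96 × √(0.782 × 0.218/35) = 14 points under the alternative, and 16 points under the null (0.621).
- If that share is compared with the null, use the null conditional on being progression-free at first dose, averaged over actual first-dose dates. This is about 0.62 under the assumptions above, not 0.50.
- Label the 24-month PFS estimate descriptive, or drop it.
- Reconcile 18 months with 2 years of enrollment. Restate events and power in section 10.2 for the accrual and progression follow-up that tumor assessments will deliver, or make no powered claim.

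The alternative is to keep Day 1 and reword section 2.2. That needs a progression assessment at 12 months after Day 1, which the plan does not have, and gives 63-64% power if PFS ends there.

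Cost: wording in three sections, a re-derived section 10.2 and modest programming. Transplant and first-dose dates are already needed to apply the entry window, and the transplant route adds no scan. Downsides: the stated power may become less favourable, the 24-month figure is descriptive at most, and the 12-month figure describes treated patients, not all transplanted patients.

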5.2 Treatment Duration

Study treatment consists of a maximum of 6 months of treatment. Patients must receive at least 2 cycles of nivolumab to be evaluable for efficacy.

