6. DOSE MODIFICATIONS

If toxicity occurs, the toxicity will be graded utilizing the NCI CTCAE v4.03 (https://evs.nci.nih.gov/ftp1/CTCAE/CTCAE_4.03/CTCAE_4.03_2010-06-14_QuickReference_8.5x11.pdf), and appropriate supportive care treatment will be administered to decrease the signs and symptoms thereof.

There will be no dose reduction of nivolumab; however, treatment delays are allowed. If the toxicity does not resolve to NCI CTCAE \leq Grade 1 after 28 days, then the patient should be withdrawn from the study and observed until resolution of the toxicity.

The dose modifications to be used in this study are presented in Table 1.

CONFIDENTIAL

STUDY DRUG: NIVOLUMAB

SARAH CANNON DEVELOPMENT INNOVATIONS STUDY NUMBER:

FINAL PROTOCOL DATE: 07 FEB 2020

BMT 24

VERSION 7

Table 1 **Dose Level Modifications**

Adverse Reaction	Severity*	Dose Modification
Colitis	Grade 2 diarrhea or colitis	Withhold dose ^a
	Grade 3 diarrhea or colitis	Withhold dose ^a
	Grade 4 diarrhea or colitis	Permanently discontinue
Pneumonitis	Grade 2	Withhold dose ^a
	Grade 3 or 4	Permanently discontinue
Hepatitis	AST or ALT >3 and up to 5 × the ULN or total bilirubin >1.5 and up to 3 × the ULN	Withhold dose ^a
	AST or ALT >5 × the ULN or total bilirubin > 3 × the ULN	Permanently discontinue
Hypophysitis	Grade 2 or 3	Withhold dose ^a
	Grade 4	Permanently discontinue
Adrenal Insufficiency	Grade 2	Withhold dose ^a
	Grade 3 or 4	Permanently discontinue
Type 1 Diabetes Mellitus	Grade 3 hyperglycemia	Withhold dose ^a
	Grade 4 hyperglycemia	Permanently discontinue
Nephritis and Renal Dysfunction	Serum creatinine >2.5 and up to 6 × the ULN	Withhold dose ^a
	Serum creatinine >6 × the ULN	Permanently discontinue
Rash	Grade 3	Withhold dose ^a
	Grade 4	Permanently discontinue
Encephalitis	New-onset moderate or severe neurologic signs or symptoms	Withhold dose ^a
	Immune-mediated encephalitis	Permanently discontinue
Other	Other Grade 3 adverse reaction First occurrence	Withhold dose ^a
	Recurrence of same Grade 3 adverse reactions	Permanently discontinue
	Life-threatening or Grade 4 adverse reaction	Permanently discontinue
	Requirement for 10 mg per day or greater prednisone or equivalent for more than 12 weeks	Permanently discontinue
	Persistent Grade 2 or 3 adverse reactions lasting 12 weeks or longer	Permanently discontinue

*Toxicity was graded per NCI CTCAE v. 4.03.

^a Resume treatment when adverse reaction returns to Grade 0 or 1.

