7.6 Follow-up

Patients will be followed every month (± 1 week) for 3 months and then every 3 months thereafter from the date of last dose of nivolumab for up to 2 years. A research blood sample will be taken 1 year after the first dose of nivolumab. A phone call may be used to assess survival and to record initiation of an alternative form of treatment for lymphoma after response assessment at 1 year post-ASCT.

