11.1.5 Recording and Reporting of Adverse Events

Recording of Adverse Events

All AEs from any patient that occur during the course of the research study will be recorded in the eCRF, and the Investigator will give his or her opinion as to the relationship of the AE to the study drug treatment (i.e., whether the event is related or unrelated to study drug administration).

All AEs should be documented. A description of the event, including its date of onset and resolution, whether it constitutes a SAE or not, any action taken (e.g., changes to study treatment), and outcome, should be provided, along with the Investigator's assessment of causality (i.e., the relationship to the study treatment[s]). For an AE to be a suspected treatment-related event there should be at least a reasonable possibility of a causal relationship between the protocol treatment and the AE. Adverse events will be graded according to the NCI CTCAE v4.03, and changes will be documented.

If the AE is serious, it should be reported immediately to the Sarah Cannon Development Innovations Safety Department. Other untoward events occurring in the framework of a clinical study are to be recorded as AEs (i.e., AEs that occur prior to assignment of study treatment that are related to a protocol-mandated intervention, including invasive procedures such as biopsies, medication washout, or no treatment run-in).

Any clinically significant signs and symptoms; abnormal test findings; changes in physical examination; hypersensitivity; and other measurements that occur will be reported as an AE, and collected on the relevant eCRF screen.

Test findings will be reported as an AE if: the test result requires an adjustment in the study drug(s) or discontinuation of treatment, and/ or test findings require additional testing or surgical intervention, a test result or finding is associated with accompanying symptoms, or a test result is considered to be an AE by the Investigator.

Reporting Period for Adverse Events

All AEs, regardless of seriousness or relationship to nivolumab treatment (called study treatment), spanning from the start of study treatment until 100 calendar days after discontinuation or completion of study treatment as defined by the clinical study for that patient, are to be recorded on the corresponding screen(s) included in the eCRF.

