All AEs resulting in discontinuation from the study should be followed until resolution or stabilization. All new AEs occurring during this period must be reported and followed until resolution unless, in the opinion of the Investigator, the AE or laboratory abnormality/ies are not likely to improve because of the underlying disease. In this case, the Investigators must record his or her reasoning for this decision in the patient's medical record.

After 100 days following the completion of protocol-specific treatment or discontinuation, only AEs, SAEs, or deaths assessed by the Investigator as treatment-related are to be reported.

CONFIDENTIAL

STUDY DRUG: NIVOLUMAB

SARAH CANNON DEVELOPMENT INNOVATIONS STUDY NUMBER:

FINAL PROTOCOL DATE: 07 FEB 2020

BMT 24

VERSION 7

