11.3.4 Deaths

Deaths that occur during the protocol-specified AE reporting period that are attributed by the Investigator solely to progression of disease will be recorded on the “Study Discontinuation” eCRF screen. All other on study deaths, regardless of attribution, will be recorded on an SAE Report Form and expeditiously reported to the Sarah Cannon Development Innovations Safety Department.

When recording a SAE with an outcome of death, the event or condition that caused or contributed to the fatal outcome should be recorded as the single medical concept on the SAE Report Form and Adverse Event screen of the eCRF. If the cause of death is unknown and cannot be ascertained at the time of reporting, record “Death NOS” (Not Otherwise Specified) on the eCRF Adverse Event screen. During post-study survival follow-up, deaths attributed to progression of disease will be recorded only on the “After Progressive Disease Follow-Up” eCRF screen.

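### The PFS definition counts only deaths 'on study', a term left undefined, so a progression-free patient who dies after withdrawal from the study is neither an event nor covered by the censoring rule

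*Combined protocol and SAP*

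**What the plan says.** **The endpoint.** PFS is the only efficacy endpoint in Section 2.4.2. Section 10.4.2 runs it from the first dose to Lugano progression "or death on study. Patients who are alive and free from disease progression will be censored at the date of last tumor assessment". Death therefore carries a qualifier, and the censoring sentence applies only to the living.

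**Pointers to a narrow meaning.** No section defines *on study*. Section 11.3.4 deals first with progression deaths in the adverse event reporting period, then says "All other on study deaths, regardless of attribution, will be recorded on an SAE Report Form", and then turns to a separate phase: "During post-study survival follow-up, deaths attributed to progression of disease will be recorded only on the" follow-up screen for patients who have already progressed. Section 11.1.5 runs the adverse event period "until 100 calendar days after discontinuation or completion of study treatment"; after that, "only AEs, SAEs, or deaths assessed by the Investigator as treatment-related are to be reported".

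**Pointers to a wide meaning.** The synopsis counts two years of follow-up in the four-year study duration. Section 7.6 and the Survival row of Appendix E follow patients for up to two years from the last dose. After the one-year response assessment, "A phone call may be used to assess survival".

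**Routes off the study without progression.** Under Section 6, if toxicity has not resolved within 28 days, "the patient should be withdrawn from the study and observed until resolution of the toxicity". Section 5.3.2 requires withdrawal from the study before a patient takes another anticancer or investigational agent.

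**The concern.** A PFS definition should give every patient one of two outcomes: an event on a date, or censoring on a date. This one leaves a third group. A progression-free patient who is withdrawn from the study and later dies is not plainly a death on study. Being dead, the patient does not fit the censoring sentence either. Someone has to choose, in an open-label trial with about 16 expected events, possibly after the deaths are known.

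The error can go only one way. Treating such a death as censoring at the last scan can raise the Kaplan-Meier curve but never lower it. The group is also unlikely to be a random sample, because the Section 6 route selects patients with unresolved toxicity. At stake is the 12-month PFS that Section 10.2 sets against 50%.

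**Working it through.** **1. The plan's own figures, and whether the wording touches them.** Inputs from Section 10.2: 12-month PFS of 50% (null) and 70% (alternative), exponential times, 18 months of accrual plus 12 of follow-up, N = 36, two-sided 0.05.

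- Hazards: λ0 = −ln(0.5)/12 = 0.05776 and λ1 = −ln(0.7)/12 = 0.02972 per month; ratio 0.5146.
- Event probability: 1 − (e^(−12λ1) − e^(−30λ1))/(18λ1) = 1 − (0.7000 − 0.4100)/0.5350 = 0.4579, as stated.
- Expected events: 36 × 0.4579 = 16.48 (stated 16).
- Power of the one-sample log-rank test, with null variance in the critical value and exact variance under the alternative. Per patient: observed events 0.4579, null-expected events 0.4579/0.5146 = 0.8898, difference 0.4320, variance under the alternative 0.7567. Then Φ[(√36 × 0.4320 − 1.96 × √0.8898)/√0.7567] = 0.803, as stated.
- Dropout: 36/0.90 = 40, as stated.

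None of these depends on how a death after withdrawal is classified.

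**2. When the countable window closes under each reading.** On the narrow reading (last dose + 100 days), counted from first dose:

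| Exposure | Last dose | Window closes |
|---|---|---|
| 1 dose | day 0 | day 100 = 3.3 months |
| 2 cycles | day 14 | day 114 = 3.7 months |
| 13 doses, every 14 days | day 168 | day 268 = 8.8 months |

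All three fall before the 12- and 24-month estimates in Section 10.4.2. Section 5.2 says "Study treatment consists of a maximum of 6 months of treatment", so the latest close is about 6 + 3.3 = 9.3 months.

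The objective in Section 2.2 counts 12 months from transplant, with treatment starting on day 45 to 180. On that clock a 13-dose patient has no gap if treatment starts on day 97 or later (97 + 268 = 365). A one-dose patient has a gap of 365 − 280 = 85 days to 365 − 145 = 220 days, or 2.8 to 7.2 months.

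On the wide reading the window runs to two years after the last dose and covers both landmarks. The patient withdrawn from the study is still left out.

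**3. Effect of one omitted death.** Assume 35 treated patients (Section 5), no other censoring before month 12, exponential PFS, and a death before month 12 that is recoded as censoring at month c. Kaplan-Meier then credits that patient's 1/35 with the survival of those still at risk, so the shift is S(12)/S(c) ÷ 35 = S(12)^((12−c)/12) ÷ 35. For c = 3.29 months the exponent is 8.71/12 = 0.726.

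- True PFS 70%: 0.7^0.726 = 0.772; 0.772/35 = 2.2 points.
- True PFS 50%: 0.5^0.726 = 0.604; 0.604/35 = 1.7 points.

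The limits are c = 0 (0.7/35 = 2.0 and 0.5/35 = 1.4 points) and c near 12 (1/35 = 2.9 points).

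**4. Effect of a steady rate (assumed).** The documents give no rate of death without progression. Let q be the share of the PFS hazard that consists of such deaths and is censored. Apparent 12-month PFS is S^(1−q). The last column is simulated under the null with N = 36 and the null-variance test, censoring at the time of death.

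| q | True 50% reads | True 70% reads | Falsely favourable result |
|---|---|---|---|
| 0 | 50.0% | 70.0% | 1.8% |
| 2% | 50.7% | 70.5% | 2.3% |
| 5% | 51.8% | 71.3% | 3.1% |
| 10% | 53.6% | 72.5% | 5.5% |
| 20% | 57.4% | 75.2% | 14.4% |

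**The case against.** The best defence is that the phrase is loose rather than restrictive. The study duration includes the follow-up years, Section 7.6 assesses survival, and Section 10.4.1 distinguishes withdrawal from treatment and from study. Stopping drug is therefore not by itself leaving the study, and deaths in planned follow-up can be read as on study. The sentences that point the other way are weaker than they look. The post-study sentence in Section 11.3.4 covers only deaths from progression, in patients who would normally have a PFS event already. Section 11.1.5 is a safety-reporting rule, not an endpoint rule, and it still asks for treatment-related deaths after 100 days. Section 7.5 asks for a one-year PET-CT in early stoppers unless they progress or start new therapy. PFS is also secondary to safety.

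Most of this stands. A reader might infer that the protocol excludes every death beyond 100 days after the last dose, and that PFS is therefore overstated. The documents do not support that: no section sets such an end date, none says these patients are censored, and none gives a rate for such deaths. Nor would these patients count as successes. A censored patient leaves the risk set, so 2.9 points per death is a ceiling.

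The wide reading does not rescue patients withdrawn from the study under Sections 5.3.2 and 6. Observation until a toxicity resolves is not survival follow-up, and no section says what their later deaths mean for PFS.

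**Conclusion.** The PFS definition has a real gap, and any bias from it runs in one direction. *On study* is undefined, the sections that bear on it pull in two directions, and on either reading a progression-free death after withdrawal from the study is outside both the stated event rule and the stated censoring rule. If such deaths are left out and the patients censored at the last scan, PFS is biased upward.

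The size is unknown and may be nil. Per patient it is roughly 1.7 to 2.2 points on 12-month PFS, against a 20-point design difference, given 35 treated patients, no other censoring, exponential times and censoring at about 3.3 months. Two or three such patients would matter to the estimate; none would leave it untouched. The sample size calculation stands as it is. The change should be made because the restriction serves no evident purpose and removing it costs almost nothing.

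**What to change.** In Section 10.4.2, replace the restricted death event with death from any cause, whether or not the patient is still on treatment, on study or within the adverse event reporting period. Take death dates from the Section 7.6 survival follow-up.

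In Section 11.3.4, have the follow-up eCRF record the date and cause of every death, not only those from progression. For the rule to work in the patients at issue, Section 7.6 should also say that survival status is still sought after withdrawal under Sections 5.3.2 or 6, unless the patient has withdrawn consent.

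The cost is wording in these sections and one eCRF field. No visits are added, since survival follow-up is already planned and may be done by telephone after the one-year assessment. The PFS estimate may come out slightly less favourable. Settle the wording before any PFS analysis.
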